(*) All cycles will last for 21 days. Cycle1 starts with the first administration of anti-PD-1 treatment BI 754091. Specific PET scan procedures will take place only during Cycle1 (baseline assessment) and Cycle2 (on-treatment assessment).

(**) The informed consent for trial Participation should be signed prior to any trial procedure. Re-consenting may become necessary when new relevant information becomes available and should be conducted according to the sponsor's instructions. A separate informed consent should be signed for biobanking if agreed by the patient.

(***) When a decision is taken to discontinue all treatment drugs, the EOT visit should be done instead of the scheduled visit.

(****) After the individual patient's end of the trial the investigator should report only any occurrence of cancer of new histology, related SAEs and related AESIs of which the investigator may become aware of and only via the SAE form, please see [Section 5.2.6.2.1](#).

(*****) Completion of patient Participation and vital status collection should also be completed if the patient withdraws prematurely following treatment start (see [Section 3.3.3](#)).

- At days of any drug administration (incl. [⁸⁹Zr]Zr-BI 754111), a physical examination and vital signs (pre- and post infusions) are required.
- Laboratory assessments (hemato, chemistry, urinalysis and pregnancy test) and 12-lead Electrocardiogram (ECG) do not need to be repeated at Day1 if performed at screening within 72 hours prior to first administration of anti-PD-1 treatment BI 754091.

Clinical Trial Protocol

Proprietary confidential information © 2020 Boehringer Ingelheim International GmbH or one or more of its affiliated companies

3. Standard static diagnostic Fluorodeoxyglucose –Positron Emission Tomography (FDG-PET)/CT should be done at screening prior to first administration of anti-PD-1 treatment BI 754091. In case FDG-PET is coupled with the baseline tumor assessment, it should be done within 7 days prior to first BI 754091 administration.

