4.1.2.2 BI 754111

BI 754111 treatment will be administered at doses expected to be therapeutically active based on non-clinical and clinical data.

The first dose to be investigated is the dose recommended for the expansion phase of trial 1381-0002. This dose was selected based on the data obtained in 1381-0002 dose-escalation cohorts, where 3 to 9 patients each received BI 754111 at dose levels of 4, 20, 80, 200, 400 and 600mg in combination with a flat dose of 240mg BI 754091. No DLTs or AESIs were observed in the dose escalation Part and maximum tolerated dose (MTD) was considered not reached.

The first administration of BI 754111 treatment will take place at Cycle2 Day1. In Part 2, various doses cohorts will be investigated sequentially. In each cohort, the dose applied at Cycle2 Day1 will depend on the magnitude of the blockade observed in the previous dose cohort. It is expected to explore at least two different dose levels of BI 754111 in this trial.

From Cycle3 Day1, the dose BI 754111 dose recommended for the expansion phase of trial 1381-0002 will be applied to all patients.

The treatment will be administered via infusion q3w.

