4.1.2.4 Dose modification for BI 754111 and BI 754091 treatments

There will be no dose reductions or escalations of BI 754091 or BI 754111 in any one patient. All patients (including patients allocated to a different dose of BI 754111 treatment during the on-treatment assessment phase (Cycle2) in Part 2), will take the recommended expansion phase dose of BI 754111 (determined in the 1381-0002 trial) starting from Cycle 3 onward.

The dose may be delayed for up to 6 weeks because of AEs, following discussion with the sponsor.

If treatment is held or discontinued due to an AE(s), both BI 754091 and BI 754111 will be held or discontinued together. If treatment is to be restarted after resolution (< Grade 1 or baseline) of the AE, both BI 754091 and BI 754111 must be started together.

The study treatments BI 754091 and BI 754111 should be permanently discontinued for CTCAE Version 5.0 Grade 3 or 4 pneumonitis, Grade 3 or 4 adrenal insufficiency, Grade 3 or 4 or recurrent colitis of any grade, Grade 4 diabetes mellitus, Grade 4 hypophysitis, Grade 4 rash, any grade encephalitis, any recurrent Grade 3 or 4 AE, transaminase values >5 times the ULN or total bilirubin >3 times ULN, inability to taper steroids to 10 mg or less prednisone or equivalent within 12 weeks, or persistent Grade 2 or 3 AEs that do not recover to Grade 1 or less within 12 weeks. Additional information of management of irAEs is provided in [Appendix 10.2](#).

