4.1.4 Drug assignment and administration of doses for each patient

The tracer dose (approximately 4mg in 20mL) of [⁸⁹Zr]Zr-BI 754111 will be injected intravenously via a pump in 10 min with flushing (10 mL physiologic saline). The mass dose might be adapted as per SMC decision. The injection will take place at the department of [REDACTED] Each patient will be administered [⁸⁹Zr]Zr-BI 754111 up to 2 times during the trial, once at Cycle1 no later than Day8 and at Cycle2 after the administration of BI 754091/BI 754111 treatment, if applicable (all patients in Part 1 and only patients tested positive for tumor LAG-3 expression in Part 2).

BI 754091 will be administered via intravenous infusion at the dose of 240mg. The first administration of BI 754091 treatment will take place at Cycle1 Day1 for each patient.

BI 754111 will be administered via intravenous infusion at the recommended expansion dose per trial 1381-0002. The first administration of BI 754111 treatment will take place at Cycle2 Day1 for each patient.

In Part 2, patients tested positive for tumor LAG-3 expression will be administered a lower or a higher dose of BI 754111 treatment at Cycle2 only. The dose allocated at these patients in Cycle2 will be confirmed by the SMC.

At Cycle2 and onwards, BI 754091 and BI 754111 treatment will be administered concomitantly.

For the preparation and administration of BI 754091 and BI 754111, please refer to the instruction provided in the ISF.

For each compound, the different timepoints of administration and the different doses are summarized in the table below.

Table 4.1.4: 1 Administration of doses per study part

Treatment Cycle	Study Part	Day	Dose to be administered
Cycle1 Baseline assessment	Part 1 and Part 2	C1 Day1	BI 754091 treatment: 240mg
		No later than day8	[⁸⁹ Zr]Zr-BI 754111: 4mg or adapted mass dose
Cycle2 On-treatment assessment	Part 1	C2 Day1	BI 754091 treatment: 240mg
			BI 754111 treatment: recommended exp. dose
	Part 2	C2 Day1	[⁸⁹ Zr]Zr-BI 754111: 4mg or adapted mass dose
			BI 754091 treatment: 240mg
			BI 754111 treatment: allocated dose per SMC decision
			[⁸⁹ Zr]Zr-BI 754111: 4mg or adapted mass dose
Cycle 3 and further cycles	Part 1 and Part 2	Cx Day1	BI 754091 treatment: 240mg
			BI 754111 treatment: recommended exp. dose

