7.3.3 Safety analyses

Adverse events will be coded using the Medical Dictionary for Drug Regulatory Activities (MedDRA). Standard BI summary tables and listings will be produced. All adverse events with an onset between start of treatment (i.e. 1st administration of anti-PD-1 treatment BI 754091 at Cycle1 Day1) and the safety follow-up (FU) 30 days after the last dose of trial medications, will be assigned to the on-treatment period for evaluation. Statistical analysis and reporting of adverse events will concentrate on treatment-emergent adverse events, i.e. all adverse events occurring between start of treatment and end of the residual effect period. Adverse events that start before first drug intake and deteriorate under treatment will also be considered as 'treatment-emergent'.

All treated patients will be included in the safety analysis. In general, safety analyses will be descriptive in nature and will be based on BI standards. No hypothesis testing is planned.

Frequency, severity, and causal relationship of adverse events will be tabulated by system organ class and preferred term after coding according to the current version of MedDRA at the database lock.

Laboratory data will be analysed both quantitatively as well as qualitatively. The latter will be done via comparison of laboratory data to their reference ranges. Values outside the reference range as well as values defined as clinically relevant will be summarised. Treatment groups will be compared descriptively with regard to distribution parameters as well as with regard to frequency and percentage of patients with abnormal values or clinically relevant abnormal values.

Vital signs, physical examinations, or other safety-relevant data observed at screening, baseline, during the course of the trial and at the end-of-trial evaluation will be assessed with regard to possible changes compared to findings before start of treatment.

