6. GENERAL ANALYSIS DEFINITIONS

6.1 TREATMENT(S)

In this Phase I trial treatments are not randomised.

Patients will receive combination treatment of BI 754111 (600 mg) and ezabenlimab (240 mg). Data of study parts 1 and 2 will be reported together, grouped by (cold) blocking dose of BI 754111 (cohorts).

Table 6.1: 1 Definition of analysing treatment periods for safety analysis

Analysing Treatment Period	Start Date	Stop Date
Screening	Date of informed consent	Date/Time of the first administration of trial medication
On-treatment	Date/Time of the first administration of trial treatment	Date of the last administration of trial medication + 30 days (residual effect period)
Follow-up	Date of the last administration of trial treatment + 31 days	Date of the last per protocol visit

Note: a 30-day safety follow-up period is defined for this trial.

For safety analyses, adverse events (AEs) will be classified to one of the following time periods: “Screening”, “On-Treatment” or “Follow-up”. This will be applied for all adverse events. Detailed rule for assigning AEs to these time periods are listed below:

- If the date of informed consent \leq AE onset date $<$ date/time of first administration of [⁸⁹Zr]Zr-BI 754111, ezabenlimab or BI 754111, then the AE is assigned to “Screening”;
- If date/time of first administration of ezabenlimab or BI 754111 \leq AE onset date \leq date of last administration of [⁸⁹Zr]Zr-BI 754111, ezabenlimab or BI 754111 + 30 days, then the AE is assigned to “On-Treatment”;
- If AE onset date $>$ date of last administration of [⁸⁹Zr]Zr-BI 754111, ezabenlimab or BI 754111 + 30 days, then the AE is assigned to “Follow-up”

For the on-treatment period, the nominal trial medication assigned at the beginning of the first treatment cycle (Cycle 3) will be used as label of the analysing treatment. In cases where patients stop treatment before Cycle 3, the actual treatment doses applied in Cycles 1 and 2 will be used as label. Tables for the on-treatment period will contain a “total” column, representing all doses of trial medication combined.

The first treatment cycle starts with the first administration of any trial medication and lasts for 21 days. Treatment cycles generally consist of 21 days.

Adverse Events (AEs) that have onset date during the Screening or Follow-Up periods will be displayed in separate listings from those occurred during the on-treatment period. Listings of AEs will not present a “total” category.

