7.8.1 Adverse Events

The analyses of AEs will be descriptive in nature. All analyses will be based on the number of patients with AEs and not on the number of AEs. The analysis will be based on current BI standards ([5](#)). AEs will be coded using the most recent version of MedDRA. The severity of

AEs was assessed according to the Common Terminology Criteria for Adverse Events (CTCAE) Version 5.0. AEs will be analyzed as reported by the investigator and pooled independent of CTCAE version used if applicable.

For analysis multiple AE occurrence data on the CRF will be collapsed into an AE provided that all of the following applies:

- All AE attributes are identical (Low Level term (LLT), severity, action taken, therapy required, seriousness, reason for seriousness, relationship, outcome, AE of special interest (AESI)).
- The occurrences were time-overlapping or time-adjacent (time-adjacency of 2 occurrences is given if the second occurrence started on the same day or on the day after the end of the first occurrence).

Unless otherwise specified, the analyses of AEs will be based on the concept of treatment-emergent AEs, where a treatment-emergent AE has an onset in the analysing treatment period. For a definition of treatment refer to [Section 6.1](#). The AE analysis will be based on the on-treatment period which starts with the date of the first administration of study medication and ends 30 days after the last administration of study medication. AEs with an onset date in the screening period (time between informed consent date and date of the first administration of study medication) or follow-up period (time after the on-treatment period) will be listed separately.

AEs will be reported with start day and end day as calculated from the first day of treatment with study medication. For listings displaying AEs during the screening or follow-up period, the start and stop day are calculated from the start of the respective analysis period.

An overall summary of AEs will be presented.

Adverse events will be displayed by the initial dose of study medication administered on the first day of treatment.

The frequency of patients with adverse events during on-treatment period will be summarised by treatment, primary system organ class (SOC) and preferred term (PT), and will be sorted by the highest CTCAE grade. Separate tables will be provided for patients with:

- AEs by highest CTCAE grade
- Serious AEs (SAEs) by highest CTCAE grade

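### AE and laboratory tables pool Cycle 1, before any BI 754111 treatment dose, with later cycles, and none of the SAP's three conflicting column rules separates the phases

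*SAP*

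**What the plan says.** **Period.** SAP Table 6.1:1 has one on-treatment period. It starts at "Date/Time of the first administration of trial treatment" and ends 30 days after the last administration. SAP 7.8.1 repeats this: "The AE analysis will be based on the on-treatment period which starts with the date of the first administration of study medication". Protocol 7.3.3 fixes the start as the "1st administration of anti-PD-1 treatment BI 754091 at Cycle1 Day1". SAP 7.8.2 applies the same period to laboratory values.

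**Dosing.** Protocol 4.1.4 states: "The first administration of BI 754111 treatment will take place at Cycle2 Day1 for each patient". Cycle 1 consists of BI 754091 and, by Day 8, the radiolabelled tracer, which carries 4 mg of BI 754111 (Protocol 4.1.2.1 and 6.1). In Part 2 the Cycle 2 dose may differ between cohorts. From Cycle 3 every patient receives the same recommended dose (Protocol 4.1.2.2), which the SAP gives as 600 mg.

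**Columns.** The SAP gives three rules:
1. Section 6.1, general: data of both parts are reported "grouped by (cold) blocking dose of BI 754111 (cohorts"), that is, by Cycle 2 dose.
2. Section 6.1, on-treatment tables: the label is the nominal Cycle 3 medication, or the actual Cycle 1 and 2 doses for a patient who stops before Cycle 3.
3. Sections 7.8 and 7.8.1: patients are analysed by initial treatment, and adverse events are shown by the dose given on the first treatment day.

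Section 6.1 also calls Cycle 3 the first treatment cycle, and then says the first treatment cycle begins with the first administration of any trial medication.

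**The concern.** The on-treatment period covers three phases: BI 754091 plus tracer, the combination at the cohort's Cycle 2 dose, and the combination at the common dose. Each patient gets one column for all of it, so every rule puts some events under a regimen the patient was not receiving.

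The tables are descriptive, but column assignment still decides what they say. Protocol 7.3.3 plans a descriptive comparison of treatment groups for laboratory data. Adverse events are tabulated by highest CTCAE grade and laboratory values by worst grade, so one Cycle 1 finding can fix a patient's cell for the whole period. Cohorts may hold as few as 2 patients (Protocol 3.1 and 3.2), where one patient is 1/2 = 50 percentage points. The trial also ended early (SAP 4).

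Infusion reactions are a case in point. Protocol 1.4 reports them in about 7% of patients on the combination and in none on BI 754091 alone, with 2 events at 20 mg BI 754111. Cycle 1 is the only phase in which a reaction to the tracer can be seen without a BI 754111 treatment dose. The planned infusion-related table pools Cycle 1 with all later cycles.

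**Working it through.** The documents state no figure for this point, so there is none to reproduce. The check is date arithmetic plus a comparison of the three rules.

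**Inputs**
- On-treatment start: Cycle 1 Day 1 (Protocol 7.3.3, SAP Table 6.1:1).
- Cycle length: "All cycles will last for 21 days" (Protocol Flow Chart footnote).
- BI 754111 treatment: "The first administration of BI 754111 treatment will take place at Cycle2 Day1" (Protocol 4.1.2.2).
- End of period: last dose + 30 days (SAP Table 6.1:1).
- Number of cycles started, k: not given, so a range is assumed.

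**Time before BI 754111 treatment**

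Cycle 2 Day 1 falls on study day 1 + 21 = 22, so Days 1 to 21 come before it. Without delay the last dose is on Day 21(k−1) + 1, and the period lasts 21(k−1) + 31 days. The share is 21 / [21(k−1) + 31].

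| k | On-treatment days | Days before BI 754111 treatment | Share |
|---|---|---|---|
| 2 | 52 | 21 | 40% |
| 3 | 73 | 21 | 29% |
| 4 | 94 | 21 | 22% |
| 6 | 136 | 21 | 15% |
| 18 | 388 | 21 | 5% |

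Protocol 4.1.2.4 allows delay: "The dose may be delayed for up to 6 weeks because of AEs". If the full 6 weeks fell before Cycle 2 (an assumption), 21 + 42 = 63 days would precede BI 754111 treatment. With two cycles the share would be 63/(52 + 42) = 63/94 = 67%.

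**Where events land**

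| Rule | Cycle 1 event | Combination event |
|---|---|---|
| Cycle 2 blocking dose | Under a BI 754111 dose not yet given | Correct in Cycle 2; from Cycle 3 wrong for any cohort whose Cycle 2 dose was not the common dose |
| Nominal Cycle 3 medication (patient reaches Cycle 3) | Under 600 mg BI 754111 plus 240 mg BI 754091, not yet given | Correct from Cycle 3; in Cycle 2 wrong if a different dose was given |
| Initial dose on first day | Under BI 754091 240 mg, without mention of the tracer | Under BI 754091 alone |

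**Why a single cut is not enough**

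Suppose everything after Cycle 2 Day 1 were shown by Cycle 2 dose. With k = 3 that phase has 73 − 21 = 52 days, of which 52 − 21 = 31 (60%) follow the Cycle 3 dose. With k = 6 it has 136 − 21 = 115 days, of which 115 − 21 = 94 (82%) do. For cohorts on another Cycle 2 dose, those days would again carry the wrong label. A second cut at the Cycle 3 dose is needed.

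**The case against.** The strongest reply is that safety tables by BI 754111 dose are not established. The blocking-dose sentence is a general reporting rule. The rules written for safety point to the Cycle 3 label or the initial dose, and final display labels are deferred to the ADS Plan. The period follows the protocol, a total column is planned, and no hypothesis is tested. All individual data are listed, and adverse events carry start and end days, so in a trial of at most 40 patients Cycle 1 events can be picked out by hand. Cycle 1 is not free of BI 754111 either, since the tracer contains 4 mg.

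Most of this stands, and it rules out several stronger readings that a reader might infer:

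- **That toxicity by BI 754111 dose is overstated under any rule.** The initial-dose rule creates no BI 754111 dose column, and the Cycle 3 rule gives one common label to all patients who reach Cycle 3.
- **That Cycle 1 safety is never shown.** It is in the listings; what is missing is a summary.
- **That 40% of events are misplaced.** The figure is calendar time. The documents give no event rate by cycle.
- **That patients who stop in Cycle 1 inflate a BI 754111 treatment column.** Their whole period precedes BI 754111 treatment, but they never receive a treatment dose, and SAP 6.1 labels them by actual doses.
- **That the SAP departs from the protocol's window.** It does not.

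The reply does not reconcile the three rules, and listings do not correct a summary table whose column label is wrong for part of the period.

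**Conclusion.** The point holds in a limited form. One unsplit period is combined with three incompatible column rules, and no rule separates the phases in the summary tables. Two rules place Cycle 1 events and worst grades under a BI 754111 treatment dose not yet given; the third places combination events under BI 754091 alone.

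The size is 21 days per patient who goes on to Cycle 2: 40%, 29% or 15% of on-treatment time for 2, 3 or 6 cycles started. This assumes no delay and a last dose on Day 1 of the last cycle. The effect on event counts cannot be derived from the documents. The primary PET endpoint is not affected. The change is a cheap improvement to the safety reporting and should be made.

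**What to change.** Choose one grouping rule for all safety tables, remove the other two from SAP 6.1, 7.8 and 7.8.1, and correct the wording that calls Cycle 3 the first treatment cycle. Then split the on-treatment row of Table 6.1:1:

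- **Cycle 1 (BI 754091 + tracer):** up to the first BI 754111 treatment infusion, or last dose + 30 days if there is none. One pooled column; all treated patients are the denominator.
- **Cycle 2:** from that infusion until the Cycle 3 dose, or last dose + 30 days if there is none. Columns by the Cycle 2 BI 754111 dose received; patients who received it are the denominator.
- **Cycle 3 onward:** from the Cycle 3 dose to last dose + 30 days. One column under the common dose; patients who received the Cycle 3 dose are the denominator.
- **Whole period:** kept with the protocol's window, as a total column only.

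State that a laboratory sample taken before an infusion belongs to the preceding phase, and how an event that worsens across a boundary is counted.

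The cost is extra analysis periods in the ADS Plan and a few more tables with small denominators; the dosing, onset and sampling dates are already collected. The split describes timing, not cause: SAP 7.8.1 accepts that immune-mediated events can begin more than 30 days after treatment, so late events due to BI 754091 can still fall in the later phases. A footnote should say so.

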7.8 SAFETY ANALYSIS

All safety analyses will be performed on the treated set (TS). Treated patients will be analyzed according to their initial treatment.

Analyses will be performed as defined in Section 7.3.3 of the CTP. In general, safety analyses will be descriptive in nature and will be based on BI standards. No hypothesis testing is planned.

Safety data recorded during the Residual Effect Period (REP) of 30 days will be considered as on-treatment.

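### SAP 6.1, 7.8 and 7.8.1 give incompatible rules for grouping patients in the safety tables; under the Cycle 3 rule, a column for a Cycle 2 dose other than 600 mg can hold only early stoppers

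*SAP*

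**What the plan says.** SAP 6.1 contains two grouping statements. The first reports Parts 1 and 2 together, "grouped by (cold) blocking dose of BI 754111 (cohorts"). The second concerns the on-treatment safety period: "the nominal trial medication assigned at the beginning of the first treatment cycle (Cycle 3) will be used as label of the analysing treatment". It has an exception: "In cases where patients stop treatment before Cycle 3, the actual treatment doses applied in Cycles 1 and 2 will be used as label". The next paragraph of 6.1 defines the first treatment cycle differently: "The first treatment cycle starts with the first administration of any trial medication and lasts for 21 days".

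SAP 7.8 gives a third rule for all safety analyses: "Treated patients will be analyzed according to their initial treatment". SAP 7.8.1 makes it more specific: "Adverse events will be displayed by the initial dose of study medication administered on the first day of treatment". Section 7.8.1 also refers back to 6.1 for the definition of treatment, and no sentence says which rule takes precedence.

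SAP 7.4.1 summarises the primary endpoint by Cycle 2 dose group. SAP 7.7 restricts the exposure summary to patients with at least one cycle of the nominal 600 mg plus 240 mg combination.

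**The concern.** The columns of the AE and laboratory tables depend on which sentence is programmed. They could be dose cohorts, or a single group with nothing to compare. They could also be patients who reached Cycle 3 set beside early stoppers at another dose. In that last case, column membership is decided by a post-baseline event that an adverse event can itself cause.

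The columns have a use. SAP 7.8.1 tabulates AEs by treatment, and SAP 7.8 states "Analyses will be performed as defined in Section 7.3.3 of the CTP"; that protocol section compares treatment groups descriptively on laboratory data. A reader looking for safety by Cycle 2 cohort could not find it under the Cycle 3 rule or the first-day rule.

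**Working it through.** **What varies between patients**
- Cycle 1 Day 1: BI 754091 alone for everyone (protocol 3.2). The tracer may be given from Day 1 to Day 8 (Flow Chart, footnote 7), and SAP 3 counts it as study medication. Tracer given on Day 1 is therefore the only possible first-day difference.
- Cycle 2 Day 1: first BI 754111 treatment. In Part 2 the dose may be lower or higher for LAG-3-positive patients, at Cycle 2 only (protocol 4.1.4).
- Cycle 3 onward: one common dose for all (protocol 4.1.2.2), given as 600 mg in SAP 6.1.

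**Each rule applied to each patient path** (X = a Cycle 2 dose other than 600 mg)

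| Path | Cycle 2 cohort (6.1) | Cycle 3 label (6.1) | First-day dose (7.8, 7.8.1) |
|---|---|---|---|
| No Cycle 2 dose | none | actual Cycle 1 dose: 240 mg BI 754091, plus tracer if given | 240 mg BI 754091 |
| X, stops before Cycle 3 | X | actual Cycle 1 and 2 doses, including X | 240 mg BI 754091 |
| X, reaches Cycle 3 | X | 600 + 240 mg | 240 mg BI 754091 |
| 600 mg, stops before Cycle 3 | 600 mg | actual Cycle 1 and 2 doses, including 600 mg | 240 mg BI 754091 |
| 600 mg, reaches Cycle 3 | 600 mg | 600 + 240 mg | 240 mg BI 754091 |

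Under the Cycle 3 label, dose X appears only in the row for patients who stop, so every member of an X column is an early stopper. The first-day column is the same in every row, apart from any Day 1 tracer.

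**Nominal on-treatment window.** SAP Table 6.1: 1 ends the period at "Date of the last administration of trial medication + 30 days (residual effect period"). With 21-day cycles and no delay, the dose day of cycle k is 1 + 21(k − 1).
- Last dose in Cycle 2: Day 22, and 22 + 30 = Day 52.
- Last dose in Cycle 3: Day 43, and 43 + 30 = Day 73.
- Difference: 73 − 52 = 21 days; 73/52 = 1.40.

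These are scheduled windows. Dose delays (up to 6 weeks, protocol 4.1.2.4) would move them, and death or withdrawal of consent would shorten the time actually observed.

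**Chance that an X column is empty.** Let s be the chance that a patient in cohort X stops after the Cycle 2 dose and before Cycle 3, independently of the others. With n patients in the cohort, P(empty) = (1 − s)^n. The documents give no value for s, so the range below is assumed.

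| n | s = 10% | s = 20% | s = 30% |
|---|---|---|---|
| 2 (minimum per cohort, protocol 3.1) | 81% | 64% | 49% |
| 3 | 73% | 51% | 34% |
| 10 | 35% | 11% | 3% |

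The result depends heavily on n. Protocol 1.4 allows up to 30 LAG-3-positive patients in Part 2, and final cohort sizes are not given.

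**The case against.** The strongest defence is that 6.1 moves from the general to the specific: the blocking-dose sentence governs reporting overall, and the Cycle 3 label is a deliberate safety convention. Section 7.7, which also uses the nominal 600 mg plus 240 mg combination, supports this. The reading is available within 6.1, but it does not reconcile 6.1 with 7.8 and 7.8.1. It also leaves the early-stopper column in place.

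A second defence is that initial treatment means Cycle 3, since 6.1 calls that the first treatment cycle. This fails because 6.1 also starts the first cycle at the first dose of any trial medication, and SAP 3 counts BI 754091 as study medication.

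Third, the ADS Plan, the table shells, the sponsor's AE standards or the project safety SAP may settle the display. They are not available here, so this is unknown. The SAP sentences would still disagree.

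Fourth, little depends on this. Safety is descriptive and untested, there is no secondary endpoint, and the Cycle 2 dose differs for one administration only. That stands, and it sets the severity. The study was also terminated early (SAP 4). If every Cycle 2 dose actually given was 600 mg, the early-stopper column does not arise and only the conflicting wording remains.

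Finally, labelling by the long-term dose is defensible in itself, since for patients who continue most treatment is at that dose. What is hard to defend is pairing it with an exception triggered by stopping.

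**Conclusion.** The conflict is real and its importance is minor. The rules cannot all be applied. One makes membership of any non-600 mg column depend on early stopping, and another merges all BI 754111 cohorts. The grouping of the AE tables is affected. So, it appears, is that of the AE listings: 6.1 removes only the total category from them and applies the same ADS Plan labels to tables and listings. Individual records, the Total column and the primary endpoint are unaffected.

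A reader might infer that AE rates by dose will be biased in a known direction, for example that other doses will look more toxic. The documents do not support that. Tables count patients with AEs, so AE-driven stopping could raise the rate in such a column while its shorter window lowers it. No stopping rates or final cohort sizes are given. Nor do the documents show that the trial's overall safety findings are unreliable.

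The column contents follow from the text, provided that some Cycle 2 dose differs from 600 mg. The window lengths assume dosing on schedule. The empty-column probabilities rest on an assumed s and on independence between patients.

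**What to change.** State one grouping rule in SAP 6.1 for all safety tables and listings: the Cycle 2 BI 754111 dose cohort already used in 6.1 and 7.4.1, kept whether or not Cycle 3 is reached. In addition:
- Say whether the cohort is by assigned or actual Cycle 2 dose; SAP Table 6.2: 1 foresees dispensing errors that change the actual treatment.
- Show treated patients with no Cycle 2 dose separately, with a note that this group is itself defined by early stopping.
- Say where LAG-3-negative patients are counted. They are outside dose exploration but are offered BI 754111 (protocol 3.1). Counting them by Cycle 2 dose or in their own column is acceptable.
- Delete or align the Cycle 3 label sentence and its exception (6.1), the initial-treatment sentence (7.8) and the first-day sentence (7.8.1).
- Keep one definition of the first treatment cycle, and align 7.7 and the ADS Plan.

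The cost is SAP wording, a table footnote and programming, with no new data. The footnote must state the downside: AEs from Cycle 3 onward occur at the common dose but appear under the Cycle 2 cohort. On schedule, the on-treatment days from Day 43 make up (73 − 42)/73 = 42% of the window for a patient with three cycles and (94 − 42)/94 = 55% with four. The columns would show cohort membership, not the dose at AE onset.
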